Following completion of Parts D and E (dose escalation of MOR03087 in combination with POM+DEX and LEN+DEX), the MTD and/or recommended dose in each part will be confirmed in a minimum of 6 subjects.

All cohorts:

After the first administration of study drug, the subjects will remain at the site until the end of Day 2 for safety monitoring. The subjects will not stay overnight at the site for subsequent administrations.

Based on the individual risk/benefit ratio, subjects who have an ongoing response of at least stable disease (SD) may continue treatment with the assigned study regimen until disease progression or until a maximum of 3 years after first treatment. In case subjects present with progressive disease or with no better status than SD after four treatment cycles starting with Cycle 1 Day 1, the investigator may add a low weekly dose of DEX to the regimen at his/her discretion, provided DEX is not already part of the treatment regimen.

At least 3 subjects meeting all inclusion and none of the exclusion criteria, as determined at the screening visit (see Sections 8.1 and 8.2) will be enrolled into each cohort.

Enrolment into a cohort at the next higher dose level will be based on the data generated from the previous dose level and guided by clinical review until

- the maximum planned dose has been reached, or
- the review of the safety data indicates a need to either expand the current dose level cohort to include 6 subjects or stop the dose escalation or the study, or
- the review of Part B dose level 6b and Part C dose level 6c, including available safety information from Part A dose level 8, indicates that only some of the planned weekly MOR03087 monotherapy dose escalation cohorts should be tested.

The DMC safety review will take place after the third subject enrolled into a cohort has undergone minimum safety evaluations (as defined for the "DLT Evaluable Population" in Section 15.1). The safety assessment will take into account AEs reported from Day 1 after the start of the first infusion through Day 29 before the start of the second cycle. The next cohort will only be started after the positive outcome of the safety assessment.

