4.2 Final Analysis

The analyses identified in the protocol and in this SAP will be performed after all subjects enrolled have reached the Cycle 3 Day 1 visit or end of study assessments (whichever comes first) and all relevant study data have been processed, all relevant data has been frozen and this SAP has been approved. A cut-off date will be determined for the analysis (which will be after all subjects enrolled have reached Cycle 3 Day 1 or end of study assessments) and all data available up to the cut-off date will be included into the analysis. The final analysis is also referred to as “primary completion analysis”.

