7. GENERAL ISSUES FOR STATISTICAL ANALYSIS

7.1 General Statistical Methodology

A table for disposition of all subjects (see section 8.1) will be produced for all subjects who provide informed consent, including screening failures. The Safety Population will be used for safety analysis and to analyze immunogenicity and the pharmacodynamic endpoints. The DLT Evaluable Population will be used to determine the maximum tolerated dose. Summaries for the analysis of tumor response will be provided for the Efficacy Evaluable Population and the Safety Population. Pharmacokinetic data evaluation will be not part of this SAP but described in a separate Pharmacokinetic Analysis Plan.

Each safety listing will contain a flag indicating which subjects are DLT-evaluable and which subjects are not DLT-evaluable after the subject number. All listings will be sorted by cohort (if data from more than 1 cohort is presented).

In the tables all available data of subjects including all cycles will be presented unless otherwise specified. For the AE tables presenting DLT, TEAEs by grading and SAEs, additional tables will be produced including data of the first cycle only.

Tabulations of summary statistics, graphical presentations, and statistical analyses will be performed using SAS software, Version 9.4 or later.

Continuous, quantitative variable summaries will include the number of subjects (N) (with non-missing values), mean, standard deviation, median, minimum, maximum, and first and third quartiles. First and third quartile will not be shown in by-cohort-tables (tables of type 1, see section 7.2).

Some of the descriptive summaries (as specified in the subsequent sections) will additionally include the 95%-confidence interval for the mean (absolute) change from baseline. The

confidence interval will be calculated based on the quantiles of the t-distribution assuming normal distribution of the data. Moreover, some of the descriptive summaries (as specified in subsequent sections) will include the 95%-confidence interval for the median (absolute or percentage) change from baseline. The 95%-confidence interval for the median will be calculated without any assumption on the distribution of the data (nonparametric confidence interval). [REDACTED]

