9.1 Immunogenicity Analysis

One of the primary endpoints is to evaluate the immunogenicity of MOR03087 in the Safety Population. Anti-MOR03087 antibodies will be determined by a central laboratory. The analysis will be based on both absolute numbers (number and percentage of subjects who develop anti-MOR03087 antibodies) and semiquantitative assessments (anti-MOR03087 antibody titer determination of confirmed positive samples).

The number and percentage of subjects who developed confirmed anti-MOR03087 antibodies during the study will be summarized descriptively. Rates will be calculated with respect to all subjects in the analysis group.

Exact 95%-confidence intervals will be provided for the rate of subjects who developed anti MOR03087 antibodies in combined presentations (see section 7.2).

Time to development of anti-MOR03087 antibodies [months] will be summarised descriptively using Kaplan-Meier estimates for the median, 25% quantile, and 75% quantile. 95%-confidence intervals for median, 25% quantile and 75% quantile will be provided in combined presentations.

Moreover the percentage of subjects having developed antibodies after 2, 4 and 6 months together with the corresponding 95%-confidence intervals will be estimated from the Kaplan-Meier curve for combined data.

Kaplan-Meier plots for time to development of anti-MOR03087 antibodies [months] will be provided for combined data.

Exact 95% confidence intervals and Kaplan-Meier analyses will not be produced if only very few subjects develop anti MOR03087 antibodies.

Also, if only a few subjects develop anti MOR03087 antibodies, quantitative assessments will only be presented in listings. Otherwise, summary tables may be added.

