10.2 Adverse Events

All TEAEs and SAEs will be coded using MedDRA (MedDRA Version 20.1, and updated to the newest version 23.0 for the follow-up analyses).

The body systems 'Blood and lymphatic system disorders' and 'Investigations' will be combined for the purpose of analysis. Moreover, all preferred terms from those two body systems that are subsequently listed in the same row will be combined:

- Red blood cell count decreased / Haemoglobin decreased / Haematocrit decreased / Mean cell volume decreased / Anaemia
- Fibrin D dimer increased / International normalised ratio increased / Prothrombin time shortened / Coagulopathy
- Eosinophil count increased / Eosinophilia
- Blood fibrinogen increased / Hyperfibrinogenaemia
- White blood cell count increased / Leukocytosis
- White blood cell count decreased / Leukopenia
- Lymphocyte count decreased / Natural killer cell count decreased / CD4 lymphocytes decreased / B-lymphocyte count decreased / Lymphopenia
- Monocyte count decreased / Monocytopenia
- Neutrophil count decreased / Neutropenia
- Neutrophil count increased / Neutrophilia
- Plasma cells increased / Plasmacytosis
- Platelet count decreased / Thrombocytopenia

TEAEs are defined as AEs occurring or worsening after the start (date and time) of the first study treatment (any IMP) and up to 28 days after the last study treatment including all treatment cycles (treatment emergent period). However, AEs occurring or worsening later than 28 days after the last treatment with study drug are defined as treatment emergent if these are considered to be related to the study drug.

If the start date and time of an AE are partially or completely missing, the AE will be assumed to be treatment-emergent if it cannot be definitely shown that the AE did not occur or worsen during the treatment-emergent period (worst case approach). Missing dates and times will not be replaced.

Thus, the following approach will be taken:

- If the start time of an AE is missing but the start date is complete, an AE will only be excluded from TEAEs if the start day is before the day of first treatment or the start day is after the end day of the treatment-emergent period.
- If the start time and day are missing but the start month is complete, an AE will only be excluded from TEAEs if the start month is before the month of first treatment or the start

month is after the end month of the treatment-emergent period or if stop date/time is before start of first treatment.

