The analyses by grading will be based on the NCI-CTCAE grade (version 4.0). If the NCI-CTCAE grade is not available, this will be analyzed as “Missing”.

A further summary table of the same structure will be presented which includes only AEs with a start date in the first cycle (relevant for the determination of the MTD and recommended dose). In case of incomplete start dates, an AE will be allocated to the first cycle, if it cannot be excluded that the AE started within the first cycle based on the month or year of the incomplete start date.

Summaries of incidence rates (number and percentage of subjects) and frequencies (number and percentage of AEs) of individual TEAEs by MedDRA SOC and Preferred Term will be prepared. Such summaries will be displayed for all AEs in the following categories:

- TEAEs
- TEAEs related to MOR03087
- TEAEs related to DEX
- TEAEs related to LEN
- TEAEs related to POM
- TEAEs by maximum grading according NCI-CTCAE
- DLTs
- Infusion reactions
- TEAEs leading to withdrawal of any study drug
- TEAEs that caused the subject to withdraw from the study
- TEAEs of Grade ≥ 3
- TEAEs with Grade 1 and 2
- TEAEs with Grade 3 and 4
- SAEs
- SAEs related to any treatment
- SAEs leading to death
- SAEs leading to death related to any treatment
- Non-serious TEAEs

In these summaries each subject will be counted only once within each preferred term to calculate the incidences.

The summaries of all TEAEs (summary table + TEAEs by grading) will be repeated including only TEAEs from the first cycle. The DLT summary will only be presented for the first cycle.

The time to the first TEAE will be summarized by summary statistics (n (number of subjects with event), mean, standard deviation, median, Q1, Q3, min, max) for the following TEAEs:

- Each AESI (infusion reactions \geq grade 3, cytokine release \geq grade 3, allergic reaction to MOR03087 \geq grade 3, second primary malignancies (all grades) and DLTs (all grades)
- All PTs \geq grade 3 in SOC Infections, and per PT in SOC infections with \geq grade 3
- Hematological AEs per PT \geq grade 3 (i.e. all PTs \geq grade 3 in SOC Blood and lymphatic system disorder including the ones combined with SOC Investigations as described above, and per PT in SOC Blood and lymphatic system disorder including the ones combined with SOC Investigations as described above with \geq grade 3)
- Diarrhoea \geq grade 3

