Only patients experiencing a TEAE as mentioned above will be included in the summary table. The same table will be repeated for TEAEs related to MOR03087.

Exposure-adjusted incidence rate (EAIR) will be expressed as the number of patients experiencing an AE per patient-year (PY) of exposure to treatment and is derived as the number of patients with the event divided by the sum of all patient time at risk. Time at risk is the number of years from first treatment date to first event for patients experiencing a given event, or time on treatment in years (up to 28 days after the last study treatment) for patients who did not experience the event.

EAIR will be summarized by SOC and PT for the following:

- All TEAEs
- TEAEs related to MOR03087
- TEAEs related to any study drug
- TEAEs by grading according to NCI-CTCAE
- TEAEs leading to withdrawal of any study drug
- TEAEs that caused the subject to withdraw from the study
- SAEs

In the AE listings, AEs that started prior to the administration of any study drug will be flagged as pre-treatment AEs. Any AEs that start 28 days after the last study treatment, including all treatment cycles, will be flagged as post-treatment AEs.

A special AE summary listing displaying details of the event(s) captured on the eCRF in a compact format will be provided for

- DLTs
- Infusion reactions
- AEs leading to discontinuation on MOR03087
- AEs leading to discontinuation on Pomalidomide / Lenalidomide
- SAEs

Serious adverse event reconciliation will be performed by Data Management, Clinical Research, and Premier Research Drug Safety and Pharmacovigilance via data listings, as detailed in the SAE reconciliation plan.

The sponsor will describe other AEs of special interest (i.e. infusion reactions, cytokine release, allergic reaction to MOR03087, second primary malignancies and DLTs), in addition to those reported as SAEs.

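### Time to first TEAE is summarised only in subjects with the event and without censoring, so for events with a low or steady hazard the median onset depends on exposure

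*SAP*

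**What the plan says.** SAP 10.2 sets the method: "The time to the first TEAE will be summarized by summary statistics (n (number of subjects with event), mean, standard deviation, median", followed by quartiles and range. The events are each AESI, grade 3 or higher infections, grade 3 or higher haematological events (both groups also per preferred term) and grade 3 or higher diarrhoea. It then limits the subjects: "Only patients experiencing a TEAE as mentioned above will be included in the summary table". No censoring is described. The table is repeated for MOR03087-related TEAEs.

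The observation window is tied to treatment:

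- TEAEs count "up to 28 days after the last study treatment including all treatment cycles"; later events count only if judged related (SAP 10.2).
- "In the tables all available data of subjects including all cycles will be presented unless otherwise specified" (SAP 7.1).
- Treatment may continue "until disease progression or until a maximum of 3 years after first treatment" (Protocol 7.1).
- The final analysis can be cut "after all subjects enrolled have reached the Cycle 3 Day 1 visit or end of study assessments" (SAP 4.2), and SAP 4.3 plans to re-run every analysis with longer follow-up.
- Tables are set out by cohort, by part, and by part at the recommended dose (SAP 7.2).

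Elsewhere the SAP does use event-free subjects. For EAIR they contribute time at risk: "or time on treatment in years (up to 28 days after the last study treatment) for patients who did not experience the event" (SAP 10.2). For antibody onset, SAP 7.3.2 censors subjects without antibodies, and SAP 9.1 adds Kaplan-Meier estimates: "Moreover the percentage of subjects having developed antibodies after 2, 4 and 6 months together with the corresponding" 95% confidence intervals.

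**The concern.** Onset time among cases is right-truncated by exposure: a group observed for two months can only show onsets within two months. Follow-up differs between parts by design, because Part A opened first and Parts D and E open only after dose level 7c (Protocol 8.4, SAP 3.1). At the final cut, late-enrolled parts may have about two months of data while earlier parts have much more. Treatment duration may also differ by regimen and prior therapy.

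The by-part layout and the planned re-run invite comparison of these medians. A reader could see toxicity arriving earlier in one part, or later at follow-up, when only exposure differs. At stake is the description of when toxicity occurs, not how often.

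**Working it through.** **The plan's own figures.** No figure is stated for time to first TEAE. The one numerical statement about AEs is in Protocol 15.9: with 9 subjects, an AE of probability 17% or 23% is seen at least once with probability 81% or 90%. It reproduces: 1 − 0.83⁹ = 0.813 and 1 − 0.77⁹ = 0.905. It does not bear on onset.

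**Inputs.** The windows of about 2 months (Cycle 3 Day 1) and 36 months (the 3-year cap) come from the documents. Hazards and treatment durations by part are not given, so they are assumptions here.

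**Step 1, fixed window.** With constant hazard λ per month and window t months, the probability of an event is F = 1 − exp(−λt), and the median onset among cases is −ln(1 − F/2)/λ. For λ = 0.03 and t = 2, F = 0.058 and the median is −ln(1 − 0.029)/0.03 = 0.99. For t = 36, F = 0.660 and the median is −ln(1 − 0.330)/0.03 = 13.36. The median with no truncation is ln 2/0.03 = 23.1 months.

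| Window (months) | λ = 0.01 | λ = 0.03 | λ = 0.10 | λ = 1.0 |
|---|---|---|---|---|
| 2 | 1.00 | 0.99 | 0.95 | 0.57 |
| 6 | 2.96 | 2.87 | 2.56 | 0.69 |
| 12 | 5.82 | 5.46 | 4.30 | 0.69 |
| 24 | 11.28 | 9.89 | 6.06 | 0.69 |
| 36 | 16.39 | 13.36 | 6.66 | 0.69 |

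**Step 2, risk against exposure.** With a 12-month window, a 9-fold change in hazard (0.01 to 0.09) moves the median only from 5.82 to 4.45. With hazard 0.03, a 9-fold change in window (4 to 36 months) moves it from 1.94 to 13.36. At low hazards the statistic follows exposure far more than risk.

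**Step 3, where the effect vanishes.** With a hazard of 0.5 per month in the first month and none afterwards, F = 0.393 and the median is −ln(1 − 0.197)/0.5 = 0.44 months at every window from 2 to 36 months. At λ = 1.0 it stays between 0.57 and 0.69.

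**Step 4, variable treatment duration.** In a simulation of 400,000 subjects per scenario, treatment duration was exponential plus 28 days, stopped at a data cut-off drawn uniformly from 2 to 24 months (final) or 24 to 36 months (follow-up). Results for λ = 0.03:

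| Mean treatment (months) | Final, event-only median | Follow-up, event-only median | Ratio | EAIR per patient-year, final / follow-up |
|---|---|---|---|---|
| 3 | 1.85 | 2.02 | 1.09 | 0.363 / 0.360 |
| 6 | 2.84 | 3.55 | 1.25 | 0.359 / 0.358 |
| 12 | 3.97 | 5.87 | 1.48 | 0.361 / 0.361 |
| 18 | 4.52 | 7.23 | 1.60 | 0.363 / 0.360 |

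EAIR stays at its true value of 12 × 0.03 = 0.36 throughout. Reading down a column gives the contrast between groups treated for different lengths of time at equal risk: 4.52/1.85 = 2.4-fold at the final cut and 7.23/2.02 = 3.6-fold at follow-up. At λ = 0.10 the shift between cuts is smaller, from 1.61 vs 1.71 months (mean treatment 3 months) to 3.31 vs 4.44 months (18 months).

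**The case against.** The strongest reply is that this is a descriptive table, transparent about its denominator, in a section that already handles unequal exposure. SAP 10.2 plans incidence with exact 95% intervals, tables restricted to the first cycle, and EAIR by SOC and preferred term, including by grade. Onset time is neither a primary nor a secondary endpoint. Cases-only summaries are also used openly elsewhere, such as time to first response among responders (SAP 9.2). Kaplan-Meier estimates per preferred term, in recommended-dose groups that may hold only 9 subjects, would say little.

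Much of this stands. A reader might infer that every onset time in the table mainly reflects treatment duration. The documents do not support that. DLT summaries are confined to Cycle 1 in every part and at both analyses (SAP 10.1). Infusion and allergic reactions are plausibly front-loaded, and thrombocytopenia appeared with the first dose in the marmoset study (Protocol 7.3). Nor is this the only output on AE timing: SAP 10.2 also plans first-cycle tables and lists time to onset for individual AEs, and SAP 10.3 plans a table of time to worst haematology grade. The planned lists of outputs are redacted, so others may exist.

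What the reply does not answer is that incidence and EAIR describe how often events occur. EAIR is one average rate and cannot show whether events come early or late. None of the tables described, other than the cases-only ones, gives an onset distribution beyond Cycle 1.

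**Conclusion.** The concern holds for events with a low or steady hazard over treatment, plausibly second primary malignancies and grade 3 or higher infections. For these, the event-only median depends on exposure and can differ between parts and between the two analyses at unchanged risk. It does not hold for DLTs and hardly at all for front-loaded reactions.

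The size rests on an assumed constant hazard and assumed treatment durations. At 0.03 per month, the simulated shift between final and follow-up analyses is about 1.1-fold to 1.6-fold. The spread from 1.0 to 13.4 months contrasts groups in which everyone has exactly 2 or exactly 36 months at risk. It shows the mechanism and should not be read as a forecast, because Cycle 3 Day 1 is a minimum for the last subjects enrolled and 3 years is a cap.

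A reader might also infer that the MTD, the recommended dose or the primary endpoint of AE incidence and severity is compromised. It is not: the MTD rests on DLTs in the DLT Evaluable Population, and incidence and severity have their own tables. The change is worth making because these medians will be set side by side and re-run.

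**What to change.** In SAP 10.2, for combined presentations of the Safety Population, add an onset estimate for the grouped categories only: each AESI other than DLTs, any grade 3 or higher infection, any grade 3 or higher haematological event, and grade 3 or higher diarrhoea.

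- Use cumulative incidence with death as a competing event, or 1 minus Kaplan-Meier.
- Censor event-free subjects at the end of the at-risk time already defined for EAIR, or at the data cut-off if earlier.
- State how related TEAEs starting more than 28 days after last treatment are handled, since the TEAE definition admits them but the at-risk time for event-free subjects ends there.
- Report the percentage with an event at fixed times with 95% intervals, for example the 2, 4 and 6 months of SAP 9.1, and omit the estimate where very few subjects have the event, as SAP 9.1 does.
- Keep the planned cases-only statistics, including those per preferred term, labelled *among subjects with the event; depends on exposure*.

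No new data are needed, only SAP wording and programming that reuses the EAIR at-risk rule. The cost is a few more tables. The estimates will be imprecise in small groups, and they assume that censoring at the end of treatment is not informative, which is open to doubt when treatment stops for toxicity or progression.

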10.3 Clinical Laboratory Evaluations

Safety laboratory data (hematology, serum chemistry, endocrinology, coagulation, urinalysis) will be analyzed by the respective local laboratories of each involved site.

The analysis of safety laboratory parameters will be presented separated into blood parameters (hematology, serum chemistry, endocrinology, coagulation) and urine parameters (urinalysis). All data will be listed.

The blood parameters will be transformed to SI values based on SI units to make laboratory parameters comparable between different local laboratories. The relevant reference ranges supplied by each laboratory will also be transformed to SI reference ranges for each laboratory.

Descriptive summaries of actual (absolute) values and changes from baseline values will be presented for all blood parameters.

Creatinine clearance will be calculated according to the Cockcroft-Gault formula and will be included in descriptive summaries of actual (absolute) values and changes from baseline.

Each abnormal value will be flagged to show whether it is a value below or above the reference range. For the assessment of laboratory variables, 5 categories will be used that take into account

the investigator's assessment of clinical relevance: 'clinically relevant, above', 'non-clinically relevant, above', 'within', 'non-clinically relevant, below', 'clinically relevant, below'.

The assessment of laboratory variables will be tabulated by time point for each clinical laboratory analyte (frequency tables).

If NCI-CTCAE grades are available for a clinical laboratory analyte, these will be derived according to NCI-CTCAE version 4.0 and used to present additional frequency based on NCI-CTCAE grades.

For hematology parameters, shifts in assessments from baseline to worst-post baseline will be presented based on classifications relative to the laboratory reference ranges (low/normal/high) for hematology parameters where NCI-CTCAE grades are not defined. If a subject experiences both "Low" and "High" assessments in the course of the trial, the worst post-baseline will be defined as "Low and High".

If NCI-CTCAE grades are available for a hematology parameter, frequency, shift and summary tables based on grades will be created as follows:

- Incidence of subjects with worst post-baseline grade. Each subject will be counted only for the worst grade
- Shift tables to compare baseline to the worst post-baseline value using CTCAE grades
- Summary of time to onset to worst post-baseline grade (defined as the time from treatment start to first occurrence of worst post-baseline grade): this table will present summary statistics over all grades, but only patients with a worst post-baseline grade will be included.

A separate listing will be prepared to list the time course of a laboratory parameter for a subject with any abnormal, clinically significant laboratory value (for all laboratory values irrespectively of whether NCI-CTCAE grades are available).

The investigator's assessment of categorical urinalysis variables ('normal', 'abnormal, not clinically significant', 'abnormal clinically significant') will be tabulated by time point for each urine parameter (frequency tables).

Additionally, for each of these urine parameters, shifts in assessments from baseline to Cycle 2 Day 1 and to EOS will be presented for combined data.

For all shift tables, baseline percentage will be based on the number of patients in the analysis set (N). Percentage for worst post-baseline value will be based on Baseline n for the baseline category the percentage refers to.

Laboratory values that are outside the reference range will also be flagged in the data listings, along with corresponding reference ranges.

Results of unscheduled laboratory evaluations, laboratory data of the emergency laboratory, results of urine microscopy (if available), results of the pregnancy test and screening serology results will only be included in listings.

In general, laboratory summaries except for the tables analyzing the hematology parameters (worst post-baseline assessments/grades) as described above will only include time points of Cycle 1+2 and EOS visit. For the tables analyzing the hematological parameters, all available time points will be included when deriving worst assessment/worst grade.

